4.2 Exclusion criteria

Patients fulfilling any of the following criteria are not eligible for inclusion in this study. No additional exclusions may be applied by the investigator, in order to ensure that the study population will be representative of all eligible patients.

1. Hypovolemia
2. Moderate to severe left ventricular outflow tract (including sub-valvular, valvular and supra-valvular), mitral stenosis or aortic arch obstruction (evidence of peak gradient ≥ 40 mmHg on echocardiographic or BP measurements)
3. Patients with single ventricle physiology before their Fontan operation (However, single ventricle patients post Glenn operation before their Fontan/Total cavo-pulmonary connection procedure (TCPC) can be enrolled.)
4. Patients on ECMO or VAD (excluded because of the potential interference of the extracorporeal circuit with the PK profile of serelaxin)
5. Patients with fixed pulmonary hypertension (i.e. ≥ 6 Wood Units, unable to reduce < 6 Wood Units with medical therapy)
6. Patients with blood lactate levels > 5 mmol/L at screening (excluded because of the possibility of a compensated shock)
7. Birth < 36 weeks post-conceptual age (applies only to children < 1 year old at baseline)
8. Confirmed or clinically suspected systemic infection (sepsis) or severe localized infection requiring iv antibiotics

[REDACTED]

[REDACTED]

9. Dyspnea or acute lung injury primarily due to non-cardiac causes
10. Patients with severe renal impairment, those known to have significant renal disease (e.g. significant renal dysplasia) and those having current or planned renal replacement therapy [Severe renal impairment is defined in cohort 1 to 3 as eGFR <30 mL/min/1.73m² ([Hogg et al. 2003](#)), calculated using the modified Schwartz formula (eGFR = 0.41 x height (cm)/Scr (mg/dl) - [Schwartz et al. 2009](#)) and in cohort 4 as urine output <0.5mL/kg/hour for the 24 hours prior to screening, or anuria for the 12 hours prior to screening (derived from the neonatal RIFLE criteria; [Ricci 2013](#)).]
11. Excessive use of inotropic and/or vasoactive agents at screening [vasoactive score >20; [Davidson et al. 2012](#): dose of dopamine + dobutamine + (epinephrine x 100) + (norepinephrine x 100) + (phenylephrine x 100) + (milrinone x 10) + (vasopressin x 10,000)]
12. Current or planned use of the following concomitant medications during the duration of the study drug infusion: levosimendan, nesiritide
13. Planned surgery <48 hours after screening
14. Patients with uncorrected coronary abnormalities that predispose them for myocardial ischemia
15. History or current diagnosis of cardiac electrocardiographic abnormalities indicating significant risk of safety for patients participating in the study such as:
 - Concomitant clinically significant cardiac arrhythmias, e.g., sustained ventricular tachycardia, and clinically significant second or third degree AV block, unless they are successfully managed with a pacemaker or anti-arrhythmic medication
 - History of familial long QT syndrome or known family history of Torsades de Pointes
16. Any major solid organ transplant recipient within 1 year of transplantation
17. Any major solid organ transplant recipient who presents with severe organ rejection
18. History of malignancy of any organ system (other than localized basal cell carcinoma of the skin), treated or untreated, within the past year with a life expectancy less than 1 year
19. Severe malnutrition
20. Post-operative bleeding >5 mL/kg/hour for ≥ 2 consecutive hours at any time 4 hours prior to screening
21. Any advanced, severe or unstable disease that may interfere with the primary or secondary study outcome evaluations or put the patient at special risk
22. Pregnant or nursing (lactating) women, where pregnancy is defined as the state of a female after conception and until the termination of gestation, confirmed by a positive hCG laboratory test

23. Females of child-bearing potential (girls who have reached menarche), unless they are using highly effective methods of contraception during dosing of study treatment and for the duration of the study. Highly effective contraception methods include:

- Total abstinence (when this is in line with the preferred and usual lifestyle of the subject. Periodic abstinence (e.g., calendar, ovulation, symptothermal, post-ovulation methods) and withdrawal are not acceptable methods of contraception)
- Female sterilization (have had surgical bilateral oophorectomy with or without hysterectomy) or tubal ligation at least six weeks before taking study treatment. In case of oophorectomy alone, only when the reproductive status of the woman has been confirmed by follow up hormone level assessment
- Male sterilization (at least 6 months prior to screening). For female subjects on the study, the vasectomized male partner should be the sole partner for that subject
- Use of oral (estrogen and progesterone), injected or implanted hormonal methods of contraception or placement of an intrauterine device (IUD) or intrauterine system (IUS) or other forms of hormonal contraception that have comparable efficacy (failure rate <1%), for example hormone vaginal ring or transdermal hormone contraception

In case of use of oral contraception women should have been stable on the same pill for a minimum of 3 months before taking study treatment.

Note: In case local regulations deviate from the contraception methods listed above, local regulations apply and will be described in the respective ICF.

24. Use of other investigational drugs within 30 days or 5 half-lives prior to screening, whichever is longer
25. History of hypersensitivity to serelaxin or to drugs of similar chemical classes
26. History of previous serelaxin administration
27. Inability of the patient or the parents/legal guardians to follow instructions or comply with follow-up procedures
28. Any other medical conditions that may put the patient at risk or influence study results in the Investigator's opinion, or that the Investigator deems unsuitable for the study.
29. Any clinically significant bleeding that occurs after screening and prior to infusion of study drug
30. Any indication of clinical instability, based on the investigator's judgement, preceding enrollment and/or prior to the infusion of study drug

[figure not shown]

5 Treatment

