5.5.4 Instructions for prescribing and taking study treatment

The study drug infusion will begin after informed consent has been given in writing (ICF signed by parent/guardian and patient consent or assent where applicable) and the completion of all screening/baseline procedures, and will continue for a total 48 hours (16 hour infusion per dose level). The study drug should be administered via a peripheral or central iv line or port, as soon as possible, but no more than 5 hours after enrollment (i.e. confirmation of eligibility for the study and the baseline IRT contact where a medication number is assigned). Compatible filters and syringes which have been tested and qualified for use with serelaxin, must be used to prepare and administer the study drug. [REDACTED]

The required amount of study drug will be calculated for each patient for each dose titration level and will be withdrawn from the 6 mL vials (with 3.5 mL fill) contained in the study drug kits, added to a syringe of 5% dextrose solution (10% dextrose may also be considered), and then infused at a constant rate over a period of 16 hours for each titration level. [REDACTED]

Each dose level is infused over 16 hours. Dose escalation should only occur if

- the patient does not fulfill any requirement for dose adjustment or discontinuation (see [Section 5.5.5](#) Permitted dose adjustments of study treatment) on the preceding infusion rates, and
- the investigator considers dose escalation to be safe based on his global clinical assessment, including an evaluation of the patient's hemodynamic status (including physical examination ([Section 6.5.1](#)), vital signs and hemodynamic parameters, arterio-venous oxygen extraction) and a comparison of his/her current condition with the one before starting serelaxin and before the previous dose escalation.

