administration is discontinued, regardless of the reason, the patient will continue to be followed at all study visits defined in the protocol. PK sampling should follow the schedule that is planned for after completion of the study drug (see [Section 6.6.2](#)). The exact time and date of study drug discontinuation must be recorded.

Re-administration of study drug, once terminated, is not allowed.

Changes in study drug dose must be recorded on the Dosage Administration Record CRF.

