5.5.9 Discontinuation of study treatment

Discontinuation of study treatment: The investigator should discontinue the study drug infusion for a patient if, on balance, he/she believes that continuation would be detrimental to the patient's well-being.

In particular, the study drug administration must be discontinued under the following circumstances:

- Withdrawal of informed consent-or assent
- Intolerable adverse events, thought to be related to study drug, which persist
- If the SBP falls <5th percentile for the age of the patient ([AHA PALS guidelines 2010, Kleinman 2010](#), see [Appendix 4](#)) and is considered a confirmed SBPDE, then follow the instructions outlined in [Section 5.5.5](#).
- Use of prohibited treatment as per [Section 5.5.8](#)
- Pregnancy
- Surgical intervention during the study drug infusion
- A patient should not remain in the ICU/CCU or a continuously monitored step-down Unit for the sole purpose of study drug infusion. The decision to discharge a patient from the ICU/CCU or a continuously monitored step-down unit should be made per SOC. If the serelaxin infusion is still ongoing at the time of transfer out of the ICU/CCU or a continuously monitored step-down unit, the study drug infusion is to be discontinued.

Patients who discontinue study treatment should NOT be considered withdrawn from the study. They should be followed per the visit/assessment schedule illustrated in [Table 6-1](#) until the study is complete. If they fail to return for these assessments for unknown reasons, every effort should be made to contact them as specified in [Section 5.5.11](#).

Patient withdrawal: Patients/legal guardians may voluntarily withdraw consent or assent for any reason at any time.

Withdrawal of consent or assent occurs only when a patient/legal guardian does not want to participate in the study anymore and, does not want any further visits or assessments and, does not want any further study related contacts and does not allow analysis of already obtained biologic material.

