9.4.2 Statistical model, hypothesis, and method of analysis

The PK parameters C_{ss} and CL will be mainly summarized descriptively by age cohort and dose within each dose group. A graphical presentation will be employed to show mean and individual RLX030 concentration-time profiles for each age cohort and each dose group.

The PK parameters C_{ss} and CL may be pooled across dose group (high/low-dose) within each age cohort and summarized as appropriate by dose level and age cohort for 10 $\mu\text{g}/\text{kg}/\text{day}$ and 30 $\mu\text{g}/\text{kg}/\text{day}$, respectively.

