9.4.3 Handling of missing values/censoring/discontinuations

No imputation will be done for missing values at 16, 32 or 48 hours for the estimation of Css, or at any planned time points for the by-visit summaries. Only values recorded in the data base will be used for the by-visit summaries at these time point.

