2.1 Analysis of the Pharmacokinetics (PK) data

The PK concentration will be summarized descriptively by age cohort within each dose group as well as in the overall group, and time point, using n, mean, standard deviation, coefficient of variation (CV), geometric mean, geometric CV, median, minimum, and maximum.

The PK analysis set will be used for the above analysis. This analysis will include the PK concentration data at all scheduled PK sampling time points, i.e., at 0, 2, 16, 22, 32, 40, 48 hr. during the infusion, at 0.5, 4, 8 hours post infusion or study drug discontinuation, and on day 14/day 28.

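### Exclusion 13 counts its 48 hours from screening, so it ends before the 48-hour infusion does and can admit a child who must be stopped before the C48hr sample

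*Protocol*

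**What the plan says.** Criterion 13 in Protocol section 4.2 excludes "Planned surgery <48 hours after screening". Criterion 12, directly above it, uses a different reference period: "Current or planned use of the following concomitant medications during the duration of the study drug infusion".

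Under section 5.5.4 the infusion starts once consent has been given and screening and baseline procedures are finished. It should start as soon as possible "but no more than 5 hours after enrollment", and it runs for 48 hours in three 16-hour dose steps.

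Section 5.5.9 lists the circumstances in which the drug must be stopped, among them "Surgical intervention during the study drug infusion". Section 5.5.5 does not allow a restart, and after a stop "PK sampling should follow the schedule that is planned for after completion of the study drug".

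Sections 6.6.2 and 9.4.1 estimate Css from C16hr, C32hr and C48hr, one per dose level, and derive CL as infusion rate divided by Css. Section 9.4.3 adds: "No imputation will be done for missing values at 16, 32 or 48 hours for the estimation of Css". Section 9.4.2 says Css and CL "may be pooled across dose group (high/low-dose) within each age cohort", but only for 10 and 30 µg/kg/day. SAP Addendum 1, section 2.1, lists the on-infusion PK samples "at 0, 2, 16, 22, 32, 40, 48 hr. during the infusion".

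**The concern.** The exclusion window and the infusion have the same length, which suggests that criterion 13 was meant to keep planned surgery out of the infusion. Its clock starts too early to do that. A child whose surgery is already scheduled near the end of the infusion satisfies criterion 13 but, on the planned timings, cannot complete treatment without breaching the stop rule.

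The foreseeable loss is C48hr. For the third dose step it is the only planned source of Css and CL, and the effect of age on PK is a primary objective. At 100 µg/kg/day no other group receives the dose, so pooling cannot help. The 48-hour haemodynamic reading is lost too; it is the only on-infusion top-dose time point in SAP Addendum 1 section 2.2, because the readings before each escalation belong to the two lower doses. The planned cells hold 3 to 6 patients, so one avoidable loss shows.

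**Working it through.** **Timing.** Let D be the delay from screening to infusion start.

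- Criterion 13 stops excluding at screening + 48 h.
- The infusion ends at screening + D + 48 h.
- The uncovered interval is the difference, D. The earliest planned surgery that passes falls at infusion hour 48 − D.
- The top-dose step covers hours 32 to 48, so the top-dose hours kept are (48 − D) − 32 = 16 − D.
- The 40 h PK sample is kept if 48 − D ≥ 40, that is, D ≤ 8.

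The only documented part of D is the allowance of up to 5 h from enrollment to start. The visible text gives no screening length, so the values below are assumptions shown as a range.

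| D (h) | Earliest surgery that passes (infusion hour) | Top-dose hours kept | 40 h sample | C48hr |
|---|---|---|---|---|
| 2 | 46 | 14 of 16 | kept | lost |
| 5 | 43 | 11 of 16 | kept | lost |
| 8 | 40 | 8 of 16 | kept | lost |
| 10 | 38 | 6 of 16 | lost | lost |

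If screening is read as the point of enrollment, D is still up to 5 h: the infusion then runs from 5 h to 53 h, and surgery planned at 48–53 h passes.

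**Effect of one lost C48hr on precision.** Protocol section 9.7 gives ranges that should contain the 95% CI of the geometric mean Css with about 80% probability, assuming a CV of 30%. They are reproduced by

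range = exp(± h), with h = t(0.975, n−1) × s × √[χ²(0.80, n−1) / ((n−1) × n)] and s = 0.30.

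The plan's own figures:

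- n = 6: h = 2.571 × 0.30 × √(7.289/30) = 0.380, giving (68.4%, 146.2%). The protocol states (68%, 146%).
- n = 3: h = 4.303 × 0.30 × √(3.219/6) = 0.945, giving (38.9%, 257.4%). The protocol states (39%, 257%).

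The same formula at the other sizes needed:

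- n = 2: h = 12.706 × 0.30 × √(1.642/2) = 3.454, giving (3.2%, 3164%).
- n = 5: h = 2.776 × 0.30 × √(5.989/20) = 0.456, giving (63.4%, 157.7%).
- n = 8: h = 2.365 × 0.30 × √(9.803/56) = 0.297, giving (74.3%, 134.6%).
- n = 9: h = 2.306 × 0.30 × √(11.030/72) = 0.271, giving (76.3%, 131.1%).

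| Cell | n, before → after | Range before | Range after |
|---|---|---|---|
| 100 µg/kg/day, cohorts 1 or 2, planned size | 3 → 2 | (39%, 257%) | (3%, 3160%) |
| 100 µg/kg/day, cohorts 3 or 4 | 6 → 5 | (68%, 146%) | (63%, 158%) |
| 30 µg/kg/day pooled, cohorts 1 or 2 (3 low + 3 high) | 6 → 5 | (68%, 146%) | (63%, 158%) |
| 30 µg/kg/day pooled, cohorts 3 or 4 (3 low + 6 high) | 9 → 8 | (76%, 131%) | (74%, 135%) |

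Pooling is optional. Without it, a low-dose group's 30 µg/kg/day cell has 3 patients and behaves like the first row. Using the log-normal s = √ln(1.09) = 0.294 changes little: (3.4%, 2938%) at n = 2 and (64.0%, 156.2%) at n = 5.

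**The case against.** The case against acting accepts the gap and the arithmetic and argues that the consequence is small.

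- **Frequency.** Surgery must already be planned in a window of a few hours. Only 5 h of D is documented, and the row that loses the 40 h sample rests on an assumed D. This stands.
- **Investigator discretion.** Criterion 28 lets the investigator exclude a child judged unsuitable and, being a listed criterion, it is not an added exclusion. This stands as a backstop. It does not name planned surgery or set a window, so sites may differ.
- **The worst case can be repaired.** High-dose groups in cohorts 1 and 2 may take up to 6 patients, so a lost value could be made up. The n = 2 range mostly reflects a t interval on one degree of freedom, in an analysis that is mainly descriptive. Both points are fair, but the repair costs another critically ill child.
- **Other PK data remain.** C16hr, C32hr and the samples at 0.5, 4 and 8 h after the stop are kept, as is the 40 h sample when D is at most 8 h. Section 6.6.2 permits further PK analyses. These soften the loss, but they are optional and do not replace the specified estimator; surgery may also confound the samples after the stop.
- **Haemodynamics.** The 48 h time point comes from an addendum written after database lock. Section 6.5.2 collects readings every 2 to 4 h during each dose step, so top-dose values up to the stop survive. This stands.
- **Other early stops are accepted.** Infusions may also end for transfer or a blood pressure fall. Those mostly cannot be foreseen at entry; surgery already on the schedule can.
- **Reporting.** After early termination, SAP Amendment 1 section 1 drops PK parameters. There the loss appears as a missing 48 h concentration rather than a missing Css.

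**Conclusion.** The concern holds. Whenever infusion starts after screening, criterion 13 leaves the last D hours of infusion uncovered, and it conflicts with the stop rule for any child whose surgery is planned there. On documented timing alone the gap can reach 5 h; anything longer depends on the assumed screening length. Each such child loses C48hr. The effect on precision is modest where 6 or more patients contribute, and severe only in a cell of 3. How often this would occur cannot be worked out from the documents and is probably low. It is a mis-anchored rule with a small expected effect, worth correcting because the correction is so cheap.

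**What to change.** Reword criterion 13 to exclude *planned surgery during the study drug infusion, i.e. within 48 hours after the planned start of infusion*. This matches the reference period of criterion 12 and reduces the uncovered interval to zero for any D, provided the infusion starts as planned. Whether the window should also cover the post-infusion samples is a clinical decision.

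The cost is a one-line protocol amendment. A few children with surgery scheduled in the last D hours would be excluded or deferred, which matters somewhat in a trial whose size is set by feasibility.

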5.1 Protocol requested treatment

5.1.1 Investigational treatment

Escalating doses of serelaxin will be administered in a continuous iv infusion for a total of 48 hours. Dose rates of 3 $\mu\text{g}/\text{kg}/\text{day}$, 10 $\mu\text{g}/\text{kg}/\text{day}$ and 30 $\mu\text{g}/\text{kg}/\text{day}$ will be used in the low-dose group and dose rates of 10 $\mu\text{g}/\text{kg}/\text{day}$, 30 $\mu\text{g}/\text{kg}/\text{day}$ and 100 $\mu\text{g}/\text{kg}/\text{day}$ will be used in the high-dose group.

5.2 Additional study treatment

No additional treatment beyond the investigational treatment is required for this trial. However, patients in this study will all be required to receive SOC management of AHF during both hospitalization and after discharge according to the regional or local guidelines and/or institutional standard.

5.3 Treatment arms

All enrolled patients will receive serelaxin in this open-label study.

5.4 Treatment blinding

Not applicable for this open-label study.

5.5 Treating the patient

5.5.1 Patient numbering

Each patient is uniquely identified by a Subject Number which is composed by the site number assigned by Novartis and a sequential number assigned by the investigator. Once assigned to a patient, the Subject Number will not be reused.

Upon signing the informed consent form, the patient is assigned the next sequential number as given by the investigator using the next blank eCRF book available from the electronic data capture (EDC) system.

5.5.2 Dispensing the investigational treatment

Each study site will be supplied by Novartis with open label study medication.

The investigational treatment packaging has a 2-part label. A unique medication number is printed on each part of this label.

5.5.3 Handling of study treatment

5.5.3.1 Handling of investigational treatment

Investigational treatment must be received by a designated person at the study site, handled and stored safely and properly, and kept in a secured location to which only the investigator and designees have access. Upon receipt, all investigational treatment should be stored according to the instructions specified on the labels. Clinical supplies are to be dispensed only in accordance with the protocol. Technical complaints are to be reported to the respective Novartis CPO Quality Assurance.

Medication labels will be in the local language and comply with the legal requirements of each country. They will include storage conditions for the investigational treatment but no information about the patient except for the medication number.

The investigator must maintain an accurate record of the shipment and dispensing of investigational treatment

5.5.3.2 Handling of other study treatment

Not applicable.

5.5.4 Instructions for prescribing and taking study treatment

The study drug infusion will begin after informed consent has been given in writing (ICF signed by parent/guardian and patient consent or assent where applicable) and the completion of all screening/baseline procedures, and will continue for a total 48 hours (16 hour infusion per dose level). The study drug should be administered via a peripheral or central iv line or port, as soon as possible, but no more than 5 hours after enrollment (i.e. confirmation of eligibility for the study and the baseline IRT contact where a medication number is assigned). Compatible filters and syringes which have been tested and qualified for use with serelaxin, must be used to prepare and administer the study drug. [REDACTED]

The required amount of study drug will be calculated for each patient for each dose titration level and will be withdrawn from the 6 mL vials (with 3.5 mL fill) contained in the study drug kits, added to a syringe of 5% dextrose solution (10% dextrose may also be considered), and then infused at a constant rate over a period of 16 hours for each titration level. [REDACTED]

Each dose level is infused over 16 hours. Dose escalation should only occur if

- the patient does not fulfill any requirement for dose adjustment or discontinuation (see [Section 5.5.5](#) Permitted dose adjustments of study treatment) on the preceding infusion rates, and
- the investigator considers dose escalation to be safe based on his global clinical assessment, including an evaluation of the patient's hemodynamic status (including physical examination ([Section 6.5.1](#)), vital signs and hemodynamic parameters, arterio-venous oxygen extraction) and a comparison of his/her current condition with the one before starting serelaxin and before the previous dose escalation.

If the investigator considers it unsafe, based on his/her global clinical assessment, to increase the serelaxin dose to the next dose level the patient should remain on the same dose level for another 16 hours (if tolerated). At the end of this 16 hour period, another global clinical assessment must be done to determine whether or not it is safe to escalate the dose. If it is deemed safe at that time, the dose is increased to the next dose level in the sequence of the assigned dose group (i.e. low-dose or high-dose group), not the initially planned dose level, for the remainder of the 48 hour infusion time. For example, if a patient receives 3 μ g/kg/day for 16 hours and a decision is taken to that the patient should *not* be up-titrated to the next dose level, they are to be dosed at 3 μ g/kg/day for another 16 hours, if tolerated. If after the second 16 hours at 3 μ g/kg/day, a decision is taken to up-titrate the patient, they would then

[REDACTED]

receive a 10 μ g/kg/day, for 16 hours, again if tolerated. The total infusion time of serelaxin should not exceed 48 hours regardless of dose titration. All assessments, including PK sampling, should continue per protocol even if the dose rate is not escalated.

Study drug will be dispensed only by study staff qualified to perform that function under applicable local laws and regulations for the study site(s), according to the protocol and Assessment Schedule (see [Table 6-1](#)).

All dosages prescribed and dispensed to the patient and all dose changes during the study must be recorded on the Dosage Administration Record eCRF.

